**Table 2 - Blood safety laboratory**

Clinical chemistry	Hematology	Other blood parameters
Sodium	Complete blood count (CBC)	Lipid profile
Potassium	Differential	Total cholesterol (TC)
Chloride	Platelet count	High-density lipoprotein cholesterol (HDL-C)
Carbon dioxide (bicarbonate)	Hemoglobin	Low-density lipoprotein cholesterol (LDL-C) will be calculated by Friedwald equation
Blood urea nitrogen (BUN)	Hematocrit	Non-HDLC will be calculated as the difference between TC and HDLC
Creatinine (eGFR will be calculated*)		Triglycerides (TG)
Glucose (serum)		Markers of intestinal transit and absorptiona
Alanine aminotransferase (ALT)		Vitamins: B6, B12, K, E, A
Aspartate aminotransferase (AST)		Serum folate
Total bilirubin (TB)		Ferritin
Alkaline phosphatase (ALP)		Markers of bone and calcium metabolisma
Uric acid		Calcium
Phosphorus		25-hydroxyvitamin D
Total protein		1,25-dihydroxyvitamin D
Albumin		Phosphorus
Magnesium		Parathyroid hormone (PTH)
Creatine phosphokinase (CPK)		Markers of bone resorption: N-terminal telopeptide (NTX), beta-C-terminal telopeptide (β-CTX-1)
Lactic acid dehydrogenase (LDH)		Marker of bone formation: type 1 procollagen N-terminal (P1NP), osteocalcin
		Other chemistry tests
		Amylase
		Lipase

All assessments to be performed by central laboratory.

All assessment measured in serum.

a To be collected at Baseline (Visit 3) to Week 4 (Visit 7), and at Visits 11 and 13

\*The recommended equation for estimating eGFR from serum creatinine is the 4 variable Modification of Diet in Renal Disease (MDRD) Study equation [18, 19]. The IDMS-traceable version of the MDRD Study equation is used. Either equation below may be used based on whether the laboratory reports conventional units or Standardized International (SI) units.:

Conventional Units (for use predominantly in the US): <http://nkdep.nih.gov/lab-evaluation/gfr-calculators/adults-conventional-unit.asp>

SI Units (for use predominately outside the US): <http://nkdep.nih.gov/lab-evaluation/gfr-calculators/adults-SI-units.asp>.

#### **9.2.1.4 Urinalysis**

Urinalysis (urine dipstick with microscopy) by central laboratory will be performed at Run-in (Visit 2), Baseline (Visit 3), at all on-site visits during the double-blind Treatment Period, and at Week 52. To prevent partial unblinding, the central laboratory urine dipstick will not include the measurement of urine glucose. Central urinalysis includes:

- Urine dipstick includes: specific gravity, pH, protein, blood, ketones, bilirubin, urobilinogen, nitrite, and leukocyte esterase
- Urine microscopy includes, but is not limited to: detection of formed cellular elements, casts, bacteria, yeast, parasites, and crystals in centrifuged urine sediment.

In the event of abnormal urinalysis findings suspicious of UTI, urine culture should be performed. Positive urine culture determination will be based upon the criteria of the reporting laboratory. Additionally, urine culture should be performed if at any point the Principal Investigator suspects the presence of a UTI.

In addition, urine albumin, calcium, phosphorus, glucose, magnesium, and creatinine will be assessed at Baseline (Visit 3) and selected on-site visits during treatment periods.

If the urine dipstick is positive for blood, the central laboratory will perform reflexive testing to include microscopy. Additional testing will be performed according to the judgment of the Investigator. Referral to urology/urologic evaluation is recommended for new or unexplained cases of confirmed hematuria (urology/urologic evaluation is not required where hematuria is considered to be related to diabetic nephropathy).

#### **9.2.1.5 Vital signs and physical exam**

A complete physical exam (including sitting BP and heart rate [HR], temperature, and respiratory rate) will be performed at Visit 1 (Screening), Visit 11 (Week 26), and Visit 13 (Week 52). Abbreviated physical exams (including sitting BP and HR) will be performed at all other on-site visits, with the exception of Visits 4, 5, 11, and 13 (Weeks 1, 2, 26, and 52, respectively). The abbreviated physical exam should focus on cardiac and respiratory systems, as well as any areas important for assessment of AEs if necessary.

Vital signs, including: sitting BP and HR will be assessed at Screening and Run-in (Visits 1 and 2), and all on-site visits. Three separate seated BPs and HR measurements should be taken with at least 1 minute between measurements following a 5-minute rest period and prior to phlebotomy. Full details and directions for the measurement of BP are presented in [Appendix C](#).

#### **9.2.1.6 Electrocardiogram variables**

The ECG assessment of “normal” or “abnormal” will be analyzed.

A 12-lead ECG record is performed locally at Run-in (Visit 2), Week 26 (Visit 11), and Week 52 (Visit 13).

The 12-lead ECG should be performed after at least 10 minutes in supine position and prior to the morning IMP administration. The Investigator should review the ECG and document the interpretation, sign and date it on the ECG print out and report it in the e-CRF. Each ECG trace is analyzed in comparison with the screening recorded trace. All original traces are kept as source data.

Note: Any new ECG abnormality should be rechecked for confirmation and reported as appropriate for that finding.

#### **9.2.1.7 Self-monitoring of blood glucose**

A meter for self-assessment of blood glucose will be dispensed at the Run-in visit (Visit 2). Self-monitoring blood glucose will be presented as equivalent SMPG. In addition to home measurements of SMBG, SMBG will be performed at Run-in (Visit 2), Baseline (Visit 3) and all subsequent on-site visits with the exception of Weeks 1 and 2 (Visits 4 and 5, respectively).

Patients will also receive a patient diary at all on-site Visits with the exception of Visits 4, 5, and 14. The diary will be reviewed at all on-site visits from Visit 2 to Visit 14. Self-assessed blood glucose levels will be entered in the patient diary.

Patients will be asked to self-assess blood glucose levels at least 3 times a week from the Run-in Visit (Visit 2) to the end of treatment, Visit 11.

Patients will be requested to self-assess blood glucose levels in the fasted state and whenever they experience any illnesses (eg, cold, flu), or symptoms of hyperglycemia or hypoglycemia. Symptoms of hypoglycemia may include shakiness, dizziness, sweating, hunger, headache, pale skin color, sudden moodiness or behavior changes (such as crying for no apparent reason), clumsy or jerky movements, seizure, difficulty paying attention or confusion, or tingling sensations around the mouth. Patients will be instructed to record the presence or absence of hypoglycemic episodes or hypoglycemic symptoms in the patient diary provided.

Patients will also be instructed to record SMBG values that are  $\leq 70$  mg/dL ( $\leq 3.9$  mmol/L) in the patient diary. Patients should be instructed to contact the site if fasting SMBG values over 3 consecutive days are:

- From Baseline Visit (Visit 3, Day 1) to Visit 8 (Week 8) (including value at Visit 8): FPG  $>270$  mg/dL (15.0 mmol/L)
- From Visit 8 (Week 8) to Visit 9 (Week 12) (including value at Visit 9): FPG  $>240$  mg/dL (13.3 mmol/L)
- From Visit 9 (Week 12) up to Visit 13 (Week 52): FPG/fasting SMBG  $>200$  mg/dL (11.1 mmol/L) or HbA1c  $\geq 8.5\%$  (the 8.5% criterion does not apply if the HbA1c decrease from Baseline was  $\geq 1.0\%$ ).

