## 1.2 STUDY FLOW CHART

	Screening Period		Double-Blind Treatment Period a									Extension		Follow-up a
	Screening	Run-in	3 Random- ization	4	5	6	7	8	9	10	11	12	13	14
Visit	1	2	0 Baseline	1	2	3	4	8	12	18	26	39	52	56
Week	-4	-2	0 Baseline	1	2	3	4	8	12	18	26	39	52	56
Day (window [days])		(±3)	1	7 (±5)	14 (±5)	21(±5)	28 (±5)	56 (±5)	84 (±5)	126 (±5)	182 (±5)	273(±5)	364(±5)	392(±5)
Informed consent	X													
Inclusion criteria	X													
Exclusion criteria	X		X											
Demographics	X													
Medical/Surgical History	X													
Medication History	X													
Body weight, height b	X	X	X	X	X	X	X	X	X	X	X	X	X	X
Vital signs c	X	X	X	X	X	X	X	X	X	X	X	X	X	X
Physical Exam:														
complete	X										X		X	
abbreviated d		X	X			X	X	X	X	X		X		X
Diet & exercise instruction		X	X	X	X	X	X				X		X	
Instruction on basic genito-urinary hygiene & hydration	X	X	X			X	X	X	X	X	X	X	X	
Interactive response technology (IRT) contact e	X	X	X			X	X	X	X	X	X	X	X	X
Randomization			X											
Dispense glucose meter		X												
Collect glucose meter														X
Dispense diary	X	X	X	X	X	X	X	X	X	X	X	X	X	
Collect/review diary		X	X	X	X	X	X	X	X	X	X	X	X	X
Instruction on diabetic ketoacidosis symptoms and glucose testing			X			X	X	X	X	X	X	X	X	
Dispense IMP		X	X				X	X	X	X	X	X		
IMP accounting & compliance			X	X	X	X	X	X	X	X	X	X	X	

Visit	Screening Period		Double-Blind Treatment Period a									Extension		Follow-up a
	Screening	Run-in	3 Randomization	4	5	6	7	8	9	10	11	12	13	14
Week	-4	-2	0 Baseline	1	2	3	4	8	12	18	26	39	52	56
Day (window [days])		(±3)	1	7 (±5)	14 (±5)	21(±5)	28 (±5)	56 (±5)	84 (±5)	126 (±5)	182 (±5)	273(±5)	364(±5)	392(±5)
Concomitant medication	X	X	X	X	X	X	X	X	X	X	X	X	X	X
Self-monitored blood glucose f		X	X			X	X	X	X	X	X	X	X	X
12-lead ECG g		X									X		X	
Laboratory testingh														
FPG	X		X				X	X	X	X	X	X	X	
HbA1c	X		X					X	X	X	X	X	X	
Fructosamine			X				X	X	X	X	X	X	X	
Safety laboratory i	X		X	X	X	X	X	X	X	X	X l	X	X l	X
Cystatin C			X	X	X	X	X		X		X	X	X	X
NT-proBNP			X	X	X	X	X		X		X	X	X	
Fasting lipids			X								X	X	X	
Pregnancy test (WOCBP) j	X		X				X	X	X	X	X	X	X	
FSH and/or estradiol (menopausal women only) j	X													
Sotagliflozin Plasma concentration k							X			X	X l	X	X l	

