**Table 1 - Summary of investigational medicinal products during treatment period**

IMP:	Sotagliflozin (200 mg group)	Sotagliflozin (400 mg group)	Placebo group
Name of the IMPs	Sotagliflozin (SAR439954)	Sotagliflozin (SAR439954)	Placebo
Pharmaceutical form	Sotagliflozin (SAR439954) will be supplied as 200 mg tablets	Sotagliflozin (SAR439954) will be supplied as 200 mg tablets	Placebo will be supplied as tablets (identical to sotagliflozin in appearance)
Dose, timing and route of administration	
Sotagliflozin 200 mg group:
 
One 200 mg tablet, taken orally once daily, before first meal of the day
 
One placebo tablet, taken orally once daily, before first meal of the day
	
Sotagliflozin 400 mg group:
 
Two 200 mg tablets, taken orally once daily, before first meal of the day
	
Placebo group:
 
Two placebo tablets, taken orally once daily, before first meal of the day

Duration of treatment	52 weeks following randomization		
Storage conditions	Store between +15°C and +30°C (59°F and 86°F)		

IMP = investigational medicinal product

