### 8.2.1 Rescue therapy

The thresholds values are defined as follows, depending on study period:

- From Baseline Visit (V3, Day 1) to Visit 8 (Week 8) (including value at Visit 8): FPG >270 mg/dL (15.0 mmol/L)
- From Visit 8 (Week 8) to Visit 9 (Week 12) (including value at Visit 9): FPG >240 mg/dL (13.3 mmol/L)
- From Visit 9 (Week 12) up to the EOT Period Visit 13 (Week 52) (including value at Visit 13): FPG >200 mg/dL (11.1 mmol/L) or HbA1c  $\geq 8.5\%$  (the 8.5% criterion does not apply if the HbA1c decrease from Baseline was  $\geq 1.0\%$ ).

Routine fasting SMBG (SMBG will be presented as equivalent self-monitoring plasma glucose [SMPG]) and central lab alerts on FPG (and HbA1c at Week 12 and onwards) are set up to ensure that glycemc parameters remain under predefined thresholds:

- If one fasting SMBG value exceeds the specific glycemc limit on 1 day, the patient checks it again during the 2 following days. If all the values in 3 consecutive days exceed the specific limit, the patient should contact the Investigator and **a central laboratory FPG measurement** (and HbA1c at Week 12 and onwards) **is performed** as soon as possible, preferably within 7 days to confirm the hyperglycemia.
- Upon receipt of a central laboratory rescue alert **a central laboratory re-test must be completed and confirmed as exceeding the criterion** for rescue before rescue therapy is initiated. The re-test confirmation should be performed as soon as possible, but within 7 days of receipt by unscheduled visit.

In the event that a confirmatory FPG and/or HbA1c exceed the threshold, the Investigator should ensure that no reasonable explanation exists for insufficient glucose control and in particular that:

- The increased FPG has been tested at a fasting status (ie, no food intake for  $\geq 8$  hours)
- Investigational product is given at the planned dose

- There is no intercurrent disease, which may jeopardize glycemic control (eg, infectious disease)
- Compliance to treatment is appropriate
- Compliance to diet and lifestyle is appropriate.

If any of the above can reasonably explain the insufficient glycemic control, the Investigator should consider not initiating rescue medication and should undertake appropriate action, ie:

- Assess plasma glucose in fasting condition (ie, after at least 8 hours fast)

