## 10 STUDY PROCEDURES

### 10.1 VISIT SCHEDULE

The visit schedule and procedures/assessments are listed in the Study Flow Chart ([Section 1.2](#)). The aim of this section is to provide details on how some of the procedures/assessments should be performed.

This is an out-patient study and consists of 14 on-site visits, although optional on-site and/or telephone visits can be scheduled at any time for any reason during the study whenever considered necessary by the Investigator.

The patients need to be fasting for on-site visits Visit 1 through Visit 13 (Week -4 through Week 52), unless instructed otherwise by the Investigator. Throughout the study, “fasting” is defined as 8 hours without food. **Note:** If the patient is not fasting at the visits specified above, the blood sample will not be collected and a new appointment should be given to the patient for the following day if possible, with instruction to be fasted (other procedures can be performed as scheduled). All laboratory assessments will occur prior to IMP administration on the day of the visit.

The Run-in visit (Visit 2) can be performed as soon as the results of all screening tests are available and the patient is confirmed to be eligible for participation in the study. The visit window for on-treatment Visit 4 through Visit 12 is  $\pm 5$  days. Visits 13 (EOT) should occur at the scheduled timepoint  $\pm 5$  days. For the Follow-up (Visit 14), the visit window should occur within  $\pm 5$  days, 4 weeks after last dose of IMP.

If one visit date is changed, the next visit should occur according to the original schedule, ie, calculated from the date of Baseline visit (Visit 3, Week 0).

For a complete list of procedures scheduled for each study visit please refer to the Study Flowchart ([Section 1.2](#)), which details the procedures to be performed.

All data obtained during the trial visits are reviewed by the Investigator and Sub-Investigators who are qualified in treatment of T2D and are trained on the study.

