#### **10.1.3.2 On-site Visit 13 (Week 52 – end of treatment)**

The following procedures will be performed at this visit:

- Measurement of body weight
- Vital signs. After 5 minutes resting, seated SBP, DBP, and HR will be assessed 3 times with at least 1 minute between each measurement (see [Appendix C](#) for details)
- Complete physical examination
- Diet and exercise instruction
- Instruction on DKA symptoms and basic GU hygiene and hydration (see [Appendix B](#)) is provided
- IRT to be notified of EOT
- Patient diary is collected/reviewed and a new diary is dispensed. Instructions/training are provided as needed
- IMP accounting and compliance for double-blind IMP
- Concomitant medications are assessed
- Fasting SMBG is assessed
- 12-lead ECG
- The following laboratory testing (by the central laboratory):
  - Fasting plasma glucose
  - HbA1c
  - Fructosamine
  - Clinical chemistry (including amylase, lipase, uric acid) and hematology
  - Cystatin C
  - NT-proBNP

- Fasting lipids
- Urine pregnancy testing for WOCBP
- Urinalysis (dipstick and microscopy)
- Collection of home urine for albumin, protein, creatinine, calcium, phosphorus, magnesium, glucose and albumin:creatinine ratio.
- Additional laboratory testing at this visit:
  - Pre-dose PK (plasma concentration sample for sotagliflozin and sotagliflozin-3-O-glucuronide); an additional blood sample will be collected 3 hours after IMP administration for the assessment of creatinine (for eGFR) and for assessing plasma concentration of sotagliflozin and sotagliflozin-3-O-glucuronide.
  - Markers of intestinal transit and absorption (vitamins B6, B12, K, E, and A, serum folate, and ferritin)
  - Markers of bone and calcium metabolism (serum calcium, serum 25-hydroxyvitamin D, serum 1,25-dihydroxyvitamin D, serum magnesium, serum phosphorus, serum iPTH, markers of bone resorption [serum NTX, serum  $\beta$ -CTX-1], and bone formation [serum P1NP]), osteocalcin, and ALP
- Patients are evaluated for glycemic rescue (see [Section 8.2](#))
- Evaluate for 50% increase in creatinine
- AEs/SAEs/AESI/EOSI and hypoglycemia (if any) are reported
- Patients are instructed to return to the site in the fasting state for Visit 14 (Week 56).

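### Protocol Section 9.2.1.7 ends the three-a-week home glucose schedule at Visit 11 (Week 26) and calls that visit the end of treatment, which is Visit 13 (Week 52)

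*Protocol*

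**What the plan says.** Section 9.2.1.7 of the protocol sets a minimum of three home glucose tests a week, starting at the run-in visit (Visit 2) and continuing "to the end of treatment, Visit 11".

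Elsewhere the protocol places the end of treatment later:

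- Table 1 gives the duration of treatment as "52 weeks following randomization".
- Section 10.1.3.2 is headed "On-site Visit 13 (Week 52 – end of treatment").
- Section 10.1 says "Visits 13 (EOT) should occur at the scheduled timepoint", again tying end of treatment to Visit 13.

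Two rules that depend on home readings also run to Visit 13. The last interval of the contact-the-site rule in Section 9.2.1.7 begins "From Visit 9 (Week 12) up to Visit 13 (Week 52): FPG/fasting SMBG". The last rescue threshold interval in Section 8.2.1 runs "up to the EOT Period Visit 13 (Week 52) (including value at Visit 13"). Under Section 8.2.1, after one high fasting home value, "the patient checks it again during the 2 following days". If all three days are high, the patient contacts the investigator and a central-laboratory measurement follows.

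**The concern.** The sentence gives a site two stop dates, 26 weeks apart, and no single date satisfies both. It is an operative instruction passed on to patients, so it matters which half is followed.

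If the visit number is followed, the contact and rescue thresholds stay in force through Week 52 while the stated testing frequency that feeds them lapses at Week 26. Two things would suffer:

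- **Between-visit hyperglycaemia.** The home pathway starts from a high fasting home value. After Week 26 the scheduled central fasting glucose draws are at Weeks 39 and 52. Fewer home readings between those draws means a weaker trigger.
- **Asymptomatic hypoglycaemia.** Section 10.6.1 defines it by a measured low value without symptoms. Testing prompted by symptoms cannot find it, so its detection depends largely on routine readings.

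**Working it through.** The plan gives no figure of its own here. The check is a comparison of visit numbers and period labels, with one short calculation.

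**1. Which visit is which.** The flow chart (Section 1.2) puts Visit 11 at Week 26, Day 182, and Visit 13 at Week 52, Day 364. Section 10.1.2.4 has new study drug dispensed at Visit 11, so treatment does not end there.

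**2. Where treatment ends.** Table 1, Section 10.1 and Section 10.1.3.2 all give Week 52 or Visit 13. Section 8.2.1 also attaches the end-of-treatment label to Visit 13. None of these places supports Visit 11.

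**3. What the logistics imply.** The flow-chart row "Self-monitored blood glucose f" is marked at Visits 12, 13 and 14. Diaries are dispensed through Visit 13. The glucose meter is collected only at Visit 14 (Section 10.1.4.1). These fit a Week 52 stop, so the visit number is the likely slip.

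**4. Whether footnote f settles it.** The footnote carries the same weekly minimum and stops it at the close of the Treatment Period, without a visit number. That label is used in two ways:

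- The title of Section 6.1.2 and the chart's separate Extension column make it Week 26.
- Table 1 applies it to 52 weeks, and Section 10.1.3, which covers the extension, also speaks of the treatment period.

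Because the row is marked at Visits 12 and 13, the context favours Week 52, but the wording does not exclude Week 26.

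**5. Size under the literal reading.** For a patient treated to Week 52:

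- Interval: Day 364 − Day 182 = 182 days; 182 / 7 = 26 weeks.
- Tests no longer required: 26 x 3 = 78, a lower bound because three a week is itself a minimum.
- The ±5-day windows at each visit change this little. Shortest gap: 359 − 187 = 172 days, and 172 / 7 x 3 = 73.7 tests. Longest gap: 369 − 177 = 192 days, and 192 / 7 x 3 = 82.3 tests.

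A site that follows the words about end of treatment loses none of these.

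**6. What still applies after Week 26 under the literal reading.**

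- Section 8.2.1 refers to routine fasting home testing as part of its safeguard against thresholds that run to Visit 13, but gives no frequency.
- Section 9.2.1.7 goes on to ask for fasting readings, and for readings during illness or symptoms, with no stop visit.
- On-site testing continues at Visits 12 to 14.
- Central-laboratory alerts continue.
- Section 10.3.1 separately requires regular home testing during temporary stops of study drug.

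The literal reading therefore removes the stated weekly minimum and leaves these other requests in place.

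**The case against.** The strongest reply is that little depends on the slip. A site would have to prefer one visit number over the words beside it, the contact rule in the same section, Section 8.2.1, the diaries dispensed through Visit 13 and the meter kept until Visit 14. The documents do not show how many sites would do so. The effect on reported safety is also small. SAP Section 2.4.5.1 summarises any, severe and documented symptomatic hypoglycaemia, so asymptomatic events enter only the first category and a listing. Safety is descriptive, and the instruction is the same in all blinded arms. All of this stands, and it keeps the point minor.

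A reader might infer more than the documents support, in three ways:

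- **That home readings cease after Week 26, so the home-triggered rescue pathway is switched off.** Section 8.2.1 still sets up routine fasting home testing, and Section 9.2.1.7 still asks for fasting readings without an end date. Only the stated frequency lapses.
- **That patients are unmonitored at home during temporary drug stops after Week 26.** Section 10.3.1 imposes its own requirement with no visit limit. Its cross-reference to Section 9.2.1.7 does not cancel that.
- **That the sponsor chose to relax monitoring in the extension.** The rules running to Visit 13 and the supply schedule point to a wrong visit number.

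The reply does not remove the contradiction. The remaining requests for home testing carry no frequency, and footnote f does not state one beyond doubt for Weeks 27 to 52.

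**Conclusion.** The inconsistency is real and the sentence is wrong as written. Severity is minor: it is an internal inconsistency in a monitoring instruction, and no analysis or Week 26 result changes.

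The 78-test figure rests on three conditions: the patient is treated to Week 52, the site follows the visit number, and testing would otherwise have been at the minimum frequency. It measures what the protocol stops requiring. It does not estimate tests actually lost, because patients may go on testing under the other requests. The clinical consequence is a weaker between-visit signal for high glucose and for silent lows at any site that reads the text this way. Confidence in the contradiction is high; the number of sites affected is unknown.

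**What to change.** In protocol Section 9.2.1.7, replace Visit 11 with Visit 13 (Week 52). In flow-chart footnote f, replace the reference to the end of the Treatment Period with Visit 13 (Week 52), so that both places give the same explicit stop. The copy of the footnote in SAP Appendix E can be aligned when convenient and needs no separate action.

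The cost is two wording changes. Section 15 requires ethics approval for any amendment, so the changes are best carried in the next one. No equipment, visit or analysis is added, since meters and diaries are already provided for through Week 52. The only extra burden falls on patients at a site that had stopped early. For a patient with the full 26 weeks still to run, it restores the minimum of 78 tests.
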